Title: Multicentric RCT Comparing High Purity Type I Collagen-Skin Substitute vs dHACM in Treatment of Diabetic Foot Ulcers

NCT No: NCT07046403

Date: November 09, 2025

INTRODUCTION

Diabetic foot ulcers (DFUs) represent one of the most serious complications of diabetes mellitus, affecting approximately 15-25% of diabetic patients during their lifetime [1]. It remains a major global health problem associated with infection, limb loss and increased mortality. The global burden of DFUs continues to escalate, with direct healthcare costs exceeding \$30 billion annually in the United States alone [2]. In India, the prevalence of DFUs among diabetic patients is estimated at 6.2%, with regional variations ranging from 5.6% to 9.5% [3]. The consequences of DFUs extend beyond immediate healthcare costs, as these wounds are associated with significant morbidity, prolonged hospitalizations, and increased mortality rates [4]. Recurrence is common and healing is often protracted despite best practice wound care.

The pathophysiology of DFUs involves multiple interconnected factors including peripheral neuropathy, impaired circulation, biomechanical stress, and compromised immune function [5]. Traditional wound care approaches often prove insufficient, resulting in delayed healing, increased infection rates, and ultimately, amputation in 20% of cases [6]. The complex nature of diabetic wounds necessitates advanced therapeutic interventions that can address the underlying cellular and molecular deficits.

Recent advances in regenerative medicine have introduced novel treatment modalities, including bioengineered skin substitutes and biological matrices, which have shown promise in accelerating wound healing and improving clinical outcomes [7]. Among these, high-purity type-I collagen- based skin substitutes (HPTC) and dehydrated human amnion/chorion membrane (dHACM) have emerged as promising therapeutic options [8, 9]. Type-I collagen, comprising 97% structural similarity across species, provides an optimal scaffold for cellular attachment and tissue regeneration [10]. This bioengineered collagen matrix mimics the native extracellular architecture and creates a conducive microenvironment for cell migration, proliferation, and differentiation. The inherent non-immunogenic properties of highly purified type-I collagen, which are attributed to the absence of sulphur-containing amino acids that typically trigger immune responses, make it particularly suitable and well-tolerated for wound healing applications [11].

Conversely, dHACM utilizes the natural regenerative properties of placental membranes, which have been employed clinically for over a century [12]. The amnion and chorion membranes contain growth factors, cytokines, and extracellular matrix components that facilitate wound healing through anti-inflammatory and pro-regenerative mechanisms [13].

However, processing methods may affect the bioactivity of these products, potentially limiting their therapeutic efficacy [14].

Previous single-centre studies have suggested potential advantages of HPTC over dHACM in treating chronic wounds [15, 16]. However, the evidence base remains limited, with small sample sizes and single-centre designs limiting the generalizability of findings. Furthermore, most comparative studies lack comprehensive histological analysis to elucidate the underlying mechanisms of action.

The objective of this multicentre randomized controlled trial was to compare the safety and efficacy of HPTC versus dHACM in treating DFUs, with particular emphasis on wound healing kinetics, histological parameters, and patient-centred outcomes. We desire to reiterate our previous single centre study result [17], that HPTC would demonstrate superior wound healing outcomes through enhanced cellular activity and improved tissue regeneration.

MATERIALS AND METHODS

Study Design and Setting

This prospective, multicentre, randomized, controlled, two parallel group, open-label trial based on pooled design was conducted across four tertiary care centres with study protocol approved by the institutional ethics committees of all participating centres: Adichunchanagiri Institute of Medical Sciences (AIMS), B. G. Nagara, JSS Medical College and Hospital (JSS), Mysore and Mysore Medical College and Research Institute (MMC&RI), Mysore and Rajarajeswari Medical College and Hospital (RRMCH), Bangalore, all centres in the state of Karnataka, India. The study was done under the supervision of primary investigator [name] N (AIMS) with the other principal investigators included [name], [name] and [name] M, respectively. The study protocol was approved by the institutional ethics committees of all participating centres and registered with ClinicalTrials.gov (Identifier: NCT07046403; Protocol Record Id: AIMS/IEC/206/2025). The investigators adhered to the applicable regulatory requirements and the trial was conducted in accordance with Good Clinical Practice guidelines and the Declaration of Helsinki. Written informed consent was obtained from all participants and patient confidentiality was rigorously maintained.

Patient screening and eligibility

The study population consisted of patients seeking treatment for DFUs. Eligible patients were those willing to participate and comply with scheduled visits on days 7, 14, 21, 28 (intervention period) and 35 (follow-up period). The study included two phases: screening and treatment. The screening phase aimed to determine patient eligibility for the treatment phase. During the screening, a series of assessments were conducted, including demographics, medical history, concomitant medications, vital signs, physical examination, foot ulcer history, clinical infection signs at the ulcer site, and ankle-brachial index measurement.

Inclusion criteria: Patients aged 18-75 years with type 1 or type 2 diabetes mellitus presenting with chronic foot ulcers were screened for eligibility. Target ulcer size between 5.0-20.0 cm² measured post-debridement; ulcer duration of 4-20 weeks; adequate circulation documented by ankle-brachial index (ABI) 0.7-1.3; and glycated haemoglobin (HbA1c) <12%.

Exclusion criteria included: Patients were excluded from the study if they met any of the following criteria: presence of active infection requiring systemic antibiotics, confirmed

osteomyelitis or exposed bone in the wound bed, current use of immunosuppressive therapy, diagnosis of active malignancy, pregnancy or lactation, end-stage renal disease requiring dialysis, acute Charcot foot deformity, previous amputation that would affect target ulcer offloading capacity, and participation in other investigational studies within the preceding 30 days.

Randomization and Blinding

Eligible patients were randomized 1:1 using computer-generated random sequence with variable block sizes (4, 6, 8) stratified by site. Allocation concealment was maintained using sequentially numbered opaque sealed envelopes. Due to the nature of the interventions, participants and investigators could not be blinded to treatment allocation. However, outcome assessors for wound parameters (photograph-based planimetry was performed by a central reader), histological analysis and quality of life measurements were blinded to treatment assignment.

Interventions

All participants received standardized wound care including debridement, infection control, glycaemic optimization, and pressure offloading using total contact casting or removable cast walkers. Subjects who met the study's inclusion criteria after the screening period were randomized into one of two groups:

- a. The HPTC arm (n=60) received high-purity type-I collagen-based skin substitute (Helicoll®, Encoll Corp, USA) that was carefully trimmed to precisely cover the wound bed, followed by application of standard of care (SOC) wound dressing. The reapplication schedule for HPTC was determined by the treating investigator's clinical judgment based on wound assessment and healing progress.
- b. The dHACM group (n=60) received dehydrated human amnion/chorion membrane applied according to manufacturer instructions with concurrent application of standard of care (SOC), with repeat applications performed as clinically indicated based on wound healing response.

During the four-week treatment phase, patients were re-evaluated on days 7, 14, 21, and 28. The SOC bandage in both groups included an identical three-layer dressing systems: non-adherent paraffin gauze (primary layer), absorbent gauze pads (secondary layer), and soft roll with crepe bandage (tertiary layer) - standardized 3-layer dressing system.

If the study ulcer was found to be 100% re-epithelialized during the visit, no further study procedures were conducted at that time. The patient was then scheduled for a follow-up visit after one week to confirm the healing. If complete healing was not observed, an assessment was performed to check for signs of clinical infection. If an infection was diagnosed, treatment with topical antimicrobials (betadine, chlorhexidine) or oral antibiotics was allowed, but the use of topical antibiotics (erythromycin, polymyxin, mupirocin) was prohibited.

Following the infection assessment, the ulcer was cleaned, photographed, and debrided at the investigator's discretion to ensure a clean, granulating ulcer base with minimal adherent slough. The SOC was then reapplied, and the patient was instructed to keep the bandaging dry. The patient was also advised to contact or visit the study site if the bandage became soiled or was removed. Topical antibiotics specifically on the wound were prohibited.

Systemic antibiotics were permitted when clinically needed.

Study completion

Patients completed the study four weeks after their first treatment visit. However, if a patient's study ulcer closed before the four-week mark, they were considered to have completed the study at that time. Complete healing of the study ulcer was defined as 100% re-epithelialization with no drainage. Throughout the treatment period, patients had the right to refuse participation or withdraw from the study at any time without prejudice. If a patient chose to withdraw from the study, their last recorded wound measurement was carried forward and used to calculate the change in wound size and their final outcome.

Outcome Measures

Primary Outcome:

1. Proportion of participants achieving wound size reduction at 4 weeks, measured using digital planimetry. Wound area was monitored at visits on days 7, 14, 21, 28 (intervention period) and 35 (follow-up period)

Secondary Outcomes:

1. Histological assessment of vascular incursion and wound biology was performed using punch biopsies (2mm diameter) obtained from the wound edge on day 5 post-treatment initiation. Histological parameters were evaluated using standardized scoring scales, including:

- a. vascular infiltration assessed on a 0-3 scale based on vessel count per high-power field,
- b. neo-epithelialization measured on a 0-3 scale based on epithelial migration distance from the wound edge,
- c. fibroblast activity quantified on a 0-3 scale based on α -SMA positive fibroblast count and cellular morphology,
- d. capillary density measured as vessels per mm^2 using CD31 immunohistochemical staining,
- e. inflammatory response graded on a 0-3 semi-quantitative scale, and
- f. collagen deposition assessed on a 0-3 scale using Masson's Trichrome staining.

Additional secondary outcomes included

2. Time to complete wound closure defined as 100% re-epithelialization with no drainage,
3. Percentage wound area reduction measured weekly using standardized digital photography,
4. Mean number of treatment applications representing the total applications required per participant during the 4-week treatment period,
5. Adverse events including infection and other complications monitored throughout the study period,
6. Quality of life assessed using patient-reported visual analogue scale (VAS) measuring change from baseline to follow-up week, and
7. Scar quality evaluated using the Vancouver Scar Scale at 5 weeks post-treatment

Vascularity assessment was done using biopsy on day zero of application to be compared with day five after the application of HPTC or dHCAM. For histopathological assessment, before application and on the fifth day after the application of either HPTC or dHCAM, a 2 mm punch biopsy was obtained from the wound edge extending into the wound bed under local anaesthesia (2% lidocaine without epinephrine). Biopsy samples were immediately fixed in 10% neutral buffered formalin for 24 hours, processed through graded alcohol, and embedded in paraffin blocks. Serial sections of 4 μm thickness were prepared and stained with hematoxylin and eosin (H&E) for general morphology, Masson's trichrome for collagen assessment, CD31 immunohistochemistry for capillary density evaluation, and α -SMA immunohistochemistry for fibroblast activity. Histological parameters that were evaluated included vascular infiltration, neo-epithelialization, fibroblast activity, capillary density,

inflammatory response, and collagen deposition (Table 1). All histological assessments were performed by two independent pathologists blinded to treatment allocation. Inter-observer agreement was assessed using Cohen's kappa coefficient.

Table 1: Histological parameters evaluated in the ulcer bed at baseline and on day five of application

Parameter	Measurement tool	Criteria	Score
Vascular infiltration	Assessed by counting new blood vessels (0–3 scale)	Minimal vascular ingrowth (<5 vessels/HPF)	0
		Mild infiltration (5–10 vessels/HPF)	1
		Moderate infiltration (11–20 vessels/HPF)	2
		Abundant infiltration (>20 vessels/HPF)	3
Neo-epithelialization	Measured as epithelial migration distance from wound edge (0–3 scale)	No epithelial migration	0
		Minimal migration (<25% wound coverage)	1
		Moderate migration (25–75% coverage)	2
		Extensive migration (>75% coverage)	3
Fibroblast activity	Quantified by counting α -SMA positive fibroblasts per HPF and assessment of fibroblast morphology (0–3 scale)	Sparse, inactive fibroblasts	0
		Moderate cellularity, minimal matrix production	1
		High cellularity, active-matrix synthesis	2
		Very high activity with extensive matrix deposition	3
Capillary density	Evaluated using CD31 staining, counted as vessels per mm^2 of tissue		
Inflammatory response	Graded semi-quantitatively (0–3 scale)	Minimal inflammatory infiltrate	0
		Mild chronic inflammation	1
		Moderate mixed inflammation	2
		Severe acute inflammation	3
Collagen deposition	Assessed using Masson's trichrome staining (0–3 scale)	Minimal collagen matrix	0
		Loose, immature collagen	1
		Moderate organized collagen	2
		Dense, mature collagen architecture	3

*Data presented as scoring criteria; all parameters assessed using standardized histological grading scales

Sample Size Calculation

Based on previous studies, we anticipated 85% of HPTC patients and 55% of dHACM patients would achieve wound reduction. With 80% power to detect a 25% absolute difference in complete wound closure at 5 weeks, 5% significance level, and assuming 10% dropout rate, a total of n=120 with 60 participants per group were required, pooled in from across 4 centres.

Statistical Analysis

Statistical analyses were performed using SPSS version 28.0 (IBM Corp, Armonk, NY, USA) and R version 4.3.0. Continuous variables were expressed as mean \pm standard deviation or median (interquartile range) based on normality testing using Shapiro-Wilk test. Categorical variables were presented as frequencies and percentages.

Between-group comparisons for continuous variables used independent t-tests or Mann-Whitney U tests. Chi-square or Fisher's exact tests were employed for categorical variables. Time-to-event analysis used Kaplan-Meier curves with log-rank tests. Mixed-effects models analysed repeated measures data. All analyses followed the intention-to-treat principle, with sensitivity analyses using per-protocol populations. A two-sided p-value of less than 0.05 was considered statistically significant for all analyses, with p-values less than 0.001 indicating highly significant differences between groups.

Data collection and follow-up

Demographic data, medical history, comorbidities, and baseline wound characteristics were recorded. Laboratory parameters, including haemoglobin, albumin, and glycated haemoglobin (HbA1c), were obtained at baseline and follow-up visits.

Patients were evaluated at baseline, day 5, day 7, day 14, day 21, day 28, and day 35. At each visit, wound measurements were performed using standardized digital planimetry, with wound area calculated in cm^2 . Histopathology examination results were recorded on baseline day 0 and day 5 after application. Digital photographs were taken for documentation and independent assessment. Complete wound closure was defined as 100% epithelialization without drainage or dressing requirements. Any adverse events, if they occurred, were duly noted and notified. Scar quality and durability were assessed at each visit, with patient satisfaction assessed at the fifth week, during the one-week follow-up.

Ethical Considerations

The study was conducted in accordance with ethical principles outlined in the Declaration of Helsinki. Written informed consent was obtained from all participants before enrolment.

Participant confidentiality was maintained throughout the study period. Data safety monitoring was performed by an independent committee.

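### Quality of life is listed among the outcomes with blinded assessors, but it is a VAS rated by unblinded patients, so that protection does not reach this secondary outcome

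*Combined protocol and SAP*

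**What the plan says.** Study Design and Setting describes an "open-label trial based on pooled design". Randomization and Blinding then says that "participants and investigators could not be blinded to treatment allocation". The next sentence sets out the exception. Its subject is the outcome assessors, and it covers wound parameters, where "photograph-based planimetry was performed by a central reader", then histology, and ends "quality of life measurements were blinded to treatment assignment".

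Under Outcome Measures, item 6 of the secondary outcomes reads: "Quality of life assessed using patient-reported visual analogue scale (VAS) measuring change from baseline to follow-up week".

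For histology, the text following the secondary outcomes names the blinded raters: "All histological assessments were performed by two independent pathologists blinded to treatment allocation". No section names a rater other than the patient for quality of life, or any other means of blinding it.

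The objective in the Introduction is framed "with particular emphasis on wound healing kinetics, histological parameters, and patient-centred outcomes". Statistical Analysis applies a two-sided 0.05 threshold to every analysis and does not separate supportive from confirmatory outcomes.

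**The concern.** For a patient-reported scale, the person who makes the judgement is the patient. Here the patient knows which product was applied. Any expectation about that product can enter the mark on the scale before anyone else handles the form.

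Placing quality of life beside planimetry and histology tells the reader that it has the same protection as those outcomes. It does not. What is at stake is how a between-arm difference may be read. A p-value below 0.05 on this scale could be taken as blinded evidence when it is open to reporting bias. The stated emphasis on patient-centred outcomes gives this some weight, although only one secondary outcome is involved.

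**Working it through.** The plan states no figure on this point, so there is none to reproduce. The main check sets the statements side by side.

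| Outcome | Who makes the rating | Is that person blinded, according to the documents? |
|---|---|---|
| Wound area | Central reader, from photographs | Yes (Randomization and Blinding) |
| Histology | Two independent pathologists | Yes (Randomization and Blinding; histology text under Outcome Measures) |
| Quality of life VAS | The patient (Secondary Outcomes item 6) | No: participants were not blinded (Randomization and Blinding) |

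In the first two rows the rater is separate from the patient, so blinding is possible and is described. In the third row the rater is the patient. If the assessor in the blinding sentence means the rater, that sentence conflicts with the one before it. If it means someone who hands out, collects or scores the form, there is no conflict, but the rating is still unblinded. On either reading the mark on the scale is not protected.

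**Illustration of what open-label self-rating can do.** Inputs from the documents: 60 per group and 10% dropout (Sample Size Calculation), which leaves 60 × 0.9 = 54 per group; two-sided alpha 0.05 (Statistical Analysis). Assumed input: a differential reporting shift b between arms, in SD units, with no true effect. The documents give neither a VAS standard deviation nor a bias figure, so a range is shown.

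Using the normal approximation for a two-sample comparison of means:

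- Standard error in SD units: SE = sqrt(2/n). At n = 60, sqrt(2/60) = 0.183; at n = 54, sqrt(2/54) = 0.192.
- False-positive rate = 1 − Φ(1.96 − b/SE) + Φ(−1.96 − b/SE).
- Example, b = 0.2 and n = 60: b/SE = 1.095, so the rate is 1 − Φ(0.865) + Φ(−3.055) = 0.194 + 0.001 = 0.195.

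| Assumed shift b (SD) | 60 per arm | 54 per arm |
|---|---|---|
| 0 | 5.0% | 5.0% |
| 0.1 | 8.5% | 8.1% |
| 0.2 | 19.5% | 18.0% |
| 0.3 | 37.6% | 34.4% |
| 0.4 | 59.1% | 54.7% |
| 0.5 | 78.2% | 73.8% |

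These rates describe the effect of unblinded self-rating under an assumed shift. They do not measure the effect of the blinding sentence, and correcting that sentence leaves them as they are.

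**The case against.** The strongest reply is that the blinding sentence is about assessors and can be literally true of staff who administer, collect or score the VAS. That stands. A reader might infer that the plan makes a false statement; the documents do not show this, because they do not say who the quality of life assessor was. It does not rescue the protection, since a blinded collector cannot remove expectation from a mark the patient has already made.

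A second reply is that the limitation is disclosed: the trial is called open-label, and the preceding sentence says that participants were not blinded. That is true, and a careful reader can work it out. But the next sentence points the other way for this outcome, and disclosing the open label does not cancel it.

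A third reply is that the harm is inferred. This also stands in part. Nowhere do the documents say that a quality of life difference will be presented as blinded evidence of superiority. The superiority expectation in the Introduction concerns wound healing, and quality of life is the sixth of seven secondary outcomes. The point is that the present wording leaves that misuse open.

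A fourth reply concerns the size. The shift must differ between arms to inflate the error rate. Both arms receive an active product, standardized care and the same three-layer dressing, and nothing in the documents shows that patients expected more from one product. The upper rows of the table are therefore not a prediction, and the low end belongs in view.

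**Conclusion.** The point holds for one secondary outcome. Quality of life is presented as having blinded assessment, yet the rating is made by patients who know their treatment, and no mechanism is named that could change this. The conclusion rests on the documents' own definitions and needs no outside figure.

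The size of any resulting bias is unknown. Under the assumed shifts from 0 to 0.5 SD, the false-positive rate runs from 5.0% to 78.2% at 60 per arm, or from 5.0% to 73.8% at 54 per arm; where the trial lies in that range cannot be determined, and the shift may be small. A reader might infer that the trial's evidence as a whole is less blinded than claimed. The documents do not support that on this ground: central planimetry, and with it the primary outcome, and the histology readings each have a rater separate from the patient.

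**What to change.** 1. In Randomization and Blinding, remove quality of life from the outcomes with blinded assessors. Alternatively, if it is true, state that only the person who collected or scored the form was blinded.
2. State in the same place, or at Secondary Outcomes item 6, that the VAS is rated by unblinded participants.
3. In Statistical Analysis, describe quality of life as a supportive outcome open to reporting bias, not as blinded evidence of superiority.
4. Separately, for precision and not as a cure for reporting bias, estimate the between-arm difference adjusted for baseline VAS, with a 95% confidence interval. The baseline value is already collected, because the outcome is a change from baseline.

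The document is written in the past tense, so any change to the analysis should be labelled with when it was made. Correcting the blinding statement needs no new data and can be done at any stage. The cost is a few sentences. The downside is that one secondary outcome can no longer be presented as blinded.

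### For ulcers found closed by day 21, the early-completion rule conflicts with the day-35 assessments scheduled for every patient

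*Combined protocol and SAP*

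**What the plan says.** Two sets of statements apply to a patient whose ulcer heals early.

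**Text that shortens follow-up.** The visit procedures at the end of Interventions state: "If the study ulcer was found to be 100% re-epithelialized during the visit, no further study procedures were conducted at that time". The next sentence adds: "The patient was then scheduled for a follow-up visit after one week to confirm the healing". Study completion opens with "Patients completed the study four weeks after their first treatment visit" and goes on to say that if a patient's "study ulcer closed before the four-week mark, they were considered to have completed the study at that time".

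**Text that runs to day 35.** Under Patient screening and eligibility, patients agree to comply with "scheduled visits on days 7, 14, 21, 28 (intervention period) and 35 (follow-up period". Under Outcome Measures, the primary outcome adds: "Wound area was monitored at visits on days 7, 14, 21, 28 (intervention period) and 35 (follow-up period". Data collection and follow-up lists evaluations through day 35, with planimetry and an assessment of scar quality and durability at each visit. None of these makes an exception for healed ulcers. The secondary outcomes include a 5-week Vancouver Scar Scale score and the change in VAS quality of life to the follow-up week. The Sample Size Calculation is framed on complete closure at 5 weeks.

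**Who judges the wound.** Randomization and Blinding says "participants and investigators could not be blinded to treatment allocation", but that wound-parameter assessors were blinded, with a central reader doing planimetry from photographs. In the visit procedures the photograph comes after an infection check that is triggered only when healing is incomplete: "Following the infection assessment, the ulcer was cleaned, photographed, and debrided". No section says who declares an ulcer closed.

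**The concern.** For a patient whose ulcer is found closed well before week 4, the early-completion sentence and the day-35 schedule cannot both be followed as written, and the plan does not say which governs.

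If early completion was followed, week-5 data are present for patients still unhealed (or found closed only at day 28) and absent for those who healed sooner. Healing is a post-randomization outcome that the trial expects to differ by arm. A comparison of day-35 area, 5-week scar or durability would then be made between subsets selected on response, no longer between the randomized groups.

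A lesser concern is the closure call itself. The trial is open-label. If closure was declared on site and not from a centrally read image, time to closure would lack the blinding that the plan describes for wound parameters.

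**Working it through.** **The plan's own figure.** The Sample Size Calculation gives 60 per group (120 in total) for a 25-point difference in closure at 5 weeks, with 80% power, 5% significance and 10% dropout; Statistical Analysis makes the test two-sided. Take 55% as the comparator rate and 55% + 25 points = 80% for the other arm. The plan states 55% for wound reduction, so using it for closure is an assumption.

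n per arm = [z(0.975)·√(2p̄(1−p̄)) + z(0.80)·√(p₁(1−p₁) + p₂(1−p₂))]² / (p₁−p₂)², with p̄ = (0.80 + 0.55)/2 = 0.675

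= [1.960 × √0.43875 + 0.8416 × √0.4075]² / 0.25² = (1.298 + 0.537)² / 0.0625 = 53.9, rounded up to 54; 54/0.90 = 60.

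The figure reproduces. (45% against 20% also gives 54, so the match does not identify the rates.) The present point does not change the sample size. The figure matters here only because it rests on status at 5 weeks.

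**Timing.** Confirmation visit = visit at which closure is first found + 7 days. Gap = 35 − confirmation day.

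| First found closed | Confirmation | Gap to day 35 | Scheduled weekly visits from closure through day 35 |
|---|---|---|---|
| day 7 | day 14 | 21 days | 5 (7, 14, 21, 28, 35) |
| day 14 | day 21 | 14 days | 4 (14, 21, 28, 35) |
| day 21 | day 28 | 7 days | 3 (21, 28, 35) |
| day 28 | day 35 | 0 days | 2 (28, 35) |

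Only an ulcer first found closed on day 28 has its confirmation visit on day 35. Read literally, early completion ends the study in the first column, before the plan's own confirmation visit.

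**What remains at week 5 for the first three rows.**
- If the day-35 schedule was followed, nothing is lost.
- If early completion plus one confirmation visit was followed, the last observation is on day 14, 21 or 28. Day-35 area, the 5-week scar score and durability to day 35 are then absent. Scar scores from earlier visits may exist, but not at 5 weeks.
- For VAS it depends on whether the follow-up week means the confirmation visit or day 35.
- Study completion provides carry-forward only for patients who choose to withdraw. Early completers are not withdrawals, so the handling of their later visits is undefined.

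**What is largely untouched.** The day-5 biopsy precedes the first weekly visit. For the 4-week primary outcome, an ulcer found closed on day 21 is confirmed on day 28. Ulcers found closed on day 7 or 14 may lack a day-28 measurement, but a closed ulcer counts as reduced unless it reopens.

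**The closure call.** In the visit procedures, the healed branch stops and schedules confirmation; the not-healed branch goes on to infection check, cleaning and photograph. Against that, the secondary outcomes specify weekly digital photography, and Data collection and follow-up has planimetry at each visit and photographs for independent assessment. Closure also requires no drainage (Study completion) and no need for dressings (Data collection and follow-up), and no section says who judges these.

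**The case against.** The strongest reply is that *completed the study* means only the end of the treatment phase. The plan describes two phases, screening and treatment, and labels day 35 separately as follow-up. A confirmation visit after closure shows that completion cannot mean no further assessment. The general four-week completion sentence, which uses the same verb, has to be read that way for unhealed patients or it would cancel day 35 for everyone.

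This reading is plausible, and a reader should not infer that day 35 was dropped for all patients. But the plan states it nowhere, and it does not settle what follow-up an early closer receives. Data collection and follow-up places the one-week follow-up at the fifth week, which agrees with a visit one week after closure only when closure is found on day 28.

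Two further objections succeed. The stop sentence is limited to the visit at which closure is seen. It sits awkwardly with measurement at each visit, but it does not by itself cancel day 35. And not every ulcer that closes before week 4 is affected: one that closes between the day-21 and day-28 visits and is first found closed on day 28 is confirmed on day 35.

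On blinding, a reader might infer that healed ulcers were not photographed, or that closure was called unblinded. The documents do not support either. Randomization and Blinding, the secondary outcomes and Data collection and follow-up all point to blinded reading of images at each visit. What stands is that none of them says so for the closure call.

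**Conclusion.** The point holds as an unresolved contradiction that the sponsor should settle. It applies to ulcers found closed on day 7, 14 or 21, whose confirmation visit falls 21, 14 or 7 days short of day 35 and so cannot stand in for week 5. If early completion was followed, day-35 area, the 5-week scar score and durability are missing according to healing status; VAS may be, depending on which visit was used.

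The timing assumes that closure is found at a scheduled weekly visit. The plan gives no weekly closure rates, so neither the number of patients affected nor the imbalance between arms can be computed.

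A reader might infer that week-5 data were in fact lost, or that the primary result is compromised. Neither follows: the plan does not show which text was applied, and the 4-week primary and day-5 histology are largely unaffected. Closure at 5 weeks appears in the sample size statement but is not a listed outcome, so the listed outcomes exposed are mainly secondary. The absence of an explicit blinded closure call is a subsidiary gap in the description.

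**What to change.** Reconcile Interventions, Study completion, Outcome Measures and Data collection and follow-up:

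1. Replace the early-completion wording so that all patients, healed or not, keep the already scheduled assessments to day 35. This concerns assessments only and implies nothing about treatment after closure.
2. State that a photograph is taken at the visit of apparent closure and at the confirmation visit, as at every other scheduled visit, and that the existing blinded central reader judges re-epithelialization. State who records drainage and dressing need.

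**Cost.** The visits are already in the schedule. If healed ulcers were not already photographed, the last column of the table gives 5, 4 or 3 extra photographs for closure found on day 7, 14 or 21. If they were, there are none.

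The plan is written in the past tense, so visits may be complete. In that case:

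- state which text was followed;
- have the central reader judge the existing closure images blind to arm, and report closures without an image as unblinded;
- report, by arm and healing status, how many patients have week-5 area, scar and VAS data, and which visit supplied the VAS.

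This needs only a reading of stored images and a table of counts.
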